### 12.3 Accrual Rate

The Kelly Gynecologic Oncology service at JHU sees ~50 cervical cancer cases per annum and UAB 120 per annum. Assuming half are HPV16+ and 15% are eligible to join the study then enrollment using both sites should be completed in 1 year.

### 12.4 Early Stopping Rules

This study will evaluate two different sites of TA-CIN vaccine to determine the safety

and effectiveness of TA-CIN in patients with a history of advanced cervical cancer. For each injection site, the SAE rate of 20% or more is deemed unsafe. A total of 15 patients will be enrolled, with 7-8 patients in each injection site cohort.

The study will be stopped early if there are more than two patients with SAEs observed during the study. If the SAE rate is 20% or more, there is at least 55% chance to stop the study early with 15 patients.

## **12.5 Statistical Analysis**

Adverse events will be tabulated by type and grade for each dose cohort.

The measure of immune response to the regimen will be the number of antigen-specific T cells detected by ELISPOT and/or ICC, or the simulation index of T cell proliferation, and the titer of the serum antibody as determined by ELISA. Each patient will have one measurement at baseline and 5 measurements at 5 time points after treatment. Descriptive statistics (mean and SD) and box plots will be used to summarize the immunogenicity by time point and dose cohort. Formal hypothesis testing will not be conducted to determine the ideal vaccination site. Instead, a “winner” will be picked based on the observed number of responses (42). Two-sample t-test will be used to compare the immunogenicity between two immunization sites. Data transformation will be applied if the distribution is not normal. In addition, the time course of outcomes will be investigated graphically by individual subject plots.

Cox regression analysis will be conducted to explore the association between time to disease recurrence and vaccine-induced immune response status. Patient baseline characteristics including disease stage and history of treatment will be adjusted in the analysis.

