## 12. STATISTICAL CONSIDERATIONS

### 12.1 Study Design and Endpoints

This pilot study is a single dose level assessment of the immunologic response as well as the safety and tolerability of administering TA-CIN vaccine via different sites in patients who have a history of HPV16-related cervical cancer. The primary goal is to determine the most favorable injection site for TA-CIN that exhibits the greater HPV-specific immunogenicity. The secondary goal is to evaluate the safety and tolerability profile of TA-CIN in HPV16 related cervical cancer patients.

The primary endpoint is the immune response rate at the time of the fourth follow-up measurement. The measure of immune response to the regimen will be the antigen-specific T cell response, the simulation index of T cell proliferation, and the titer of the antibody response in peripheral blood. Each patient will have one measurement at baseline and 4 measurements at 4 time points after treatment. For each individual patient, a significant immunologic response is defined as the maximum increase in antigen-specific T cell number or proliferation index after administration of TA-CIN by greater than 1.8 times the standard deviation (SD) of the baseline values, and the increase is at least 2-fold. An increase by 1.8 SD establishes a statistically significant reduction at the two-sided .10 level.

This study will evaluate two different sites, thigh and arm, for TA-CIN vaccine administration.

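### The supportive between-site t-test in Section 12.5 does not fix its outcome or scale and states no use of the baseline immune sample; a baseline-adjusted log model would settle all three at little cost.

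*Combined protocol and SAP*

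**What the plan says.** Section 12.5 gives the quantitative comparison of the two randomised sites one sentence: "Two-sample t-test will be used to compare the immunogenicity between two immunization sites". On scale it adds: "Data transformation will be applied if the distribution is not normal". It names no normality check and no transformation.

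The role of the test is limited by another sentence in the same section: "Formal hypothesis testing will not be conducted to determine the ideal vaccination site". The winner is picked on the observed number of responses.

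Baseline appears in two other places. The Section 10 calendar schedules a pre-study sample for T cells, antibody and viral load. Section 12.1 defines a responder by an increase over baseline of more than 1.8 SD that is also at least 2-fold.

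The visit is open. Section 12.1 says "The primary endpoint is the immune response rate at the time of the fourth follow-up measurement" and "Each patient will have one measurement at baseline and 4 measurements at 4 time points after treatment", yet defines response by the maximum increase. Section 12.5 says "Each patient will have one measurement at baseline and 5 measurements at 5 time points after treatment". The calendar shows six post-dose draws: Week 5, Week 9, Weeks 11-13, and Months 6, 12 and 24.

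Section 12.5 also uses a dose label for its groups: "Adverse events will be tabulated by type and grade for each dose cohort", and box plots and descriptive statistics will "summarize the immunogenicity by time point and dose cohort". Section 6.3 fixes a single dose; the groups differ only by site.

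**The concern.** Immunogenicity in the t-test sentence could mean the post-vaccination value, the change or the fold change, on a raw or a transformed scale. These are different analyses with different precision. Which t-test is the more precise depends on the correlation between baseline and follow-up, which the plan does not give. The study is open label, so choices left open could be made after the data and the allocation are known.

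A model that includes baseline makes it unnecessary to guess that correlation, and it uses a sample already on the calendar. At stake are the width and the credibility of the one quantitative site comparison that the plan prescribes. The rule that selects the site is not affected.

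**Working it through.** **The plan's own figure.** The t-test has no stated power or precision. The only design figure for the site comparison is in Section 12.2: about 70% chance of picking the right site at 65% v 45% with 7 per group. Exact enumeration of two independent binomials gives P(X_A > X_B) = 69.3%, with ties (15.8%) counted as failures. At 60% v 45% it gives 62.1%, against about 60% stated. Both reproduce, and neither depends on the t-test.

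**Inputs for the t-test.**
- Group sizes 8 and 7: 15 patients with 7-8 per site (Section 12.4). Section 12.2 says at most 7 per group.
- Baseline correlation r: not in the documents, so assumed at 0, 0.3, 0.5, 0.7, 0.8 and 0.9.
- Baseline and post values: bivariate normal with equal SD, widths in units of that SD.

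**Formulas.** The standard error factor is sqrt(1/8 + 1/7) = 0.5175. The expected sample SD is 0.981 of the true SD at 13 degrees of freedom and 0.979 at 12.
- Post value: 2.160 × 0.981 × 0.5175 = 1.10.
- Change: 1.097 × sqrt(2(1 − r)).
- Adjusted: 2.179 × 0.979 × 0.5175 × 1.043 × sqrt(1 − r²) = 1.151 × sqrt(1 − r²). The factor 1.043 is the average cost of chance baseline imbalance, the mean of sqrt(1 + T²/13) with T distributed as t on 13 degrees of freedom.

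**Mean 95% CI half-width, SD units**

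| Correlation | 0 | 0.3 | 0.5 | 0.7 | 0.8 | 0.9 |
|---|---|---|---|---|---|---|
| Post value | 1.10 | 1.10 | 1.10 | 1.10 | 1.10 | 1.10 |
| Change | 1.55 | 1.30 | 1.10 | 0.85 | 0.69 | 0.49 |
| Adjusted | 1.15 | 1.10 | 1.00 | 0.82 | 0.69 | 0.50 |

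A simulation of 40,000 trials per setting gives the same values, with type I error of 0.048-0.052 for all three methods.

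**Reading the table.**
- At 0.5 the adjusted interval is 0.997/1.097 = 0.91 of either t-test, about 9% narrower.
- Below about 0.3 there is no gain over the post value. At 0 the ratio is 1.15/1.10 = 1.05, about 5% wider.
- From about 0.8 there is no gain over change.
- The wrong t-test costs more than the wrong model: change at r = 0 is 41% wider than the post value (1.55/1.10), and the post value at r = 0.9 is more than twice as wide as change (1.10/0.49).

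**Undetectable baselines.** With 55-90% of baselines assumed to lie at the detection limit and a correlation of 0.5, the adjusted half-width is 0.933-0.965 of the post-value one, so the gain falls to about 3-7%. If 80% or 90% are at the limit, the chance that all 15 are is 0.80^15 = 3.5% or 0.90^15 = 20.6%, and the covariate is then constant.

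**Missing baselines.** At a correlation of 0.5 the adjusted half-width is 1.00 with none missing, 1.04 with one (7 v 7) and 1.10 with two (7 v 6). Two missing baselines cancel the gain over a 15-patient post-value test (1.10). This is a practical point, because Section 10 leaves research samples to the investigator's discretion, subject to supplies and safety.

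**The case against.** The strongest reply is that no decision rests on this test. Section 12.5 excludes formal testing for site selection, the t-test is valid, and the gain from adjustment is modest and rests on a correlation that nobody has stated. All of that stands, and it limits the point to a minor one. It does not answer the pre-specification gap: Section 12.5 still prescribes the comparison without saying what is compared or on what scale.

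Several stronger readings are tempting, and the documents do not support them.

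- *A reader might infer that baseline is ignored.* The sentence states no use of it, but a change-score test is not excluded, and baseline drives the responder definition in Section 12.1.
- *A reader might infer that the open choice of outcome often points to the wrong site.* At a site difference of 0.51 SD (65% v 45% read as detectability, which is itself an assumption), post value and change do favour different sites in 17-20% of trials. That is mostly sampling noise at this sample size: at a correlation of 0.5 the wrong site is favoured in 16.2% of trials by the post value and 13.8% by the adjusted model.
- *A reader might infer that the data-dependent scale inflates error.* A Shapiro-Wilk rule, which the plan does not specify, was simulated on null log-normal data with log-SD from 0.25 to 1.0. Type I error was 0.048, 0.049, 0.055 and 0.053, so there was no material inflation. The fair criticism is only that the check and transformation are unnamed.
- *A reader might infer that arm and thigh are pooled in the safety tables.* Section 1 speaks of cohorts by injection site, Section 12.4 judges the SAE rate for each site, and Section 12.5 itself goes on to name two immunization sites. The label is a slip.

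It is also fair to say that the replacement has contingencies of its own: the detection limit, a constant covariate and missing baselines. They can be written down in advance, which the present wording does not do.

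**Conclusion.** The point holds as a minor one on precision and pre-specification. The t-test is valid and subordinate to the responder count, and neither the winner rule nor its stated probabilities change. A baseline-adjusted model on a fixed log scale closes the open choices of outcome and scale. Its interval ranges from about 9% narrower than either t-test at a correlation of 0.5 to about 5% wider than the post-value test if baseline carries no information.

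These sizes assume 8 v 7 patients, normality on the analysis scale, equal SDs and the correlations listed; the documents supply no correlation or SD. The gain shrinks if many baselines are undetectable or missing. That the outcome and scale are unspecified is read directly from the text and needs no assumption.

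**What to change.** 1. Settle the visit first. Reconcile the 4, 5 and 6 post-baseline measurements in Sections 12.1, 12.5 and 10 and, within 12.1, the fixed fourth measurement with the maximum increase. The primary endpoint needs this in any case.
2. Replace the t-test and transformation sentences in 12.5 with a linear model of log post-vaccination value at that visit on site and log baseline. Apply it to ELISPOT first, following the assay order in Section 1. Set values below the assay's detection limit to that limit, and drop the covariate if it is constant.
3. Report the site ratio with its 95% CI as descriptive and subordinate to the winner rule. If any baseline is missing, give the unadjusted log post-value comparison in all patients alongside.
4. As an editorial correction only, change *dose cohort* to *injection site cohort* in both places in 12.5.

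The cost is wording in 12.5, plus the reconciliation of 12.1, 12.5 and Section 10. No samples or visits are added. One residual degree of freedom is lost, the interval may be up to about 5% wider if baseline is uninformative, and patients without a baseline leave the adjusted model.

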## **6.9 Duration of Therapy**

In the absence of treatment delays due to adverse event(s), treatment may continue for a total of three vaccinations or until one of the following criteria applies:

- Disease recurrence,
- Intercurrent illness that prevents further administration of treatment,
- Unacceptable adverse event(s) (**Section 6.6**),
- Patient or legal representative withdraws consent from the study,
- Patient is lost to follow-up,
- General or specific changes in the patient's condition render the patient unacceptable for further treatment in the judgment of the investigator,
- Non-compliance with protocol or treatment,

- Use of systemic glucocorticoids or other immune-suppressive drugs for more than 7 days required at any time after enrollment in the study, or
- Termination of the study.

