#### **6.10 Duration of Follow-Up**

Patients will be followed for 24 months after initiation of study treatment or until death, whichever occurs first. Patients who are discontinued from the study treatment due to an unacceptable drug-related AE will be monitored for safety until the resolution of the AE to  $\leq$  grade 1 or stabilization or until initiation of a new therapy for their cancer, whichever occurs first.

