## 10. STUDY CALENDAR

Test/Procedure	Pre-Study 	Week 1 Day 1	Week 2 Day 1	Week 5 Day 1	Week 6 Day 1	Week 9 Day 1	Week 10 Day 1	Week 11-13	Month 6	Month 12	Month 24
Visit Window (Days)	-60		+/- 2	+/- 5	+/- 5	+/- 5	+/- 5		+/- 28	+/- 28	+/- 28
TA-CIN Administration 		X		X		X					
Tumor HPV Testing 	X										
Informed Consent	X										
Demographics	X										
Medical History	X										
Class I and II HLA Typing 	X										
HIV/Hepatitis Panel 	X										
Physical/Pelvic Examination 	X	X		X		X		X	X	X	X
Vital Signs 	X	X		X		X		X	X	X	X
Performance Status 	X	X		X		X		X	X	X	X
Concomitant Med Review	X	X		X		X		X	X	X	X
Vaccine Site Assessment 				X		X		X			
Phone Call			X		X		X				
CBC w/Diff, Plts 	X	X		X		X		X	X	X	X
Serum Chemistry 	X	X		X		X		X	X	X	X
PET/CT, MRI or CT Scan 	X										
Evaluation of HPV16 E6, E7-Specific CD8 + T Cells 	X 			X 		X 		X 	X 	X 	X 
Evaluation of HPV16 Antibody and DNA  and HPV16 Viral Load	X 			X 		X 		X 	X 	X 	X 
Adverse Event Evaluation 											
Archived Tumor Tissue 											

Research samples will be collected at the discretion of the PI based on availability of supplies and safety of patient and staff. In order to minimize the need for research-only in-person visits, telemedicine visits may be substituted for in-person clinical trial visits or portions of clinical trial visits where determined to be appropriate and where determined by the investigator not to increase the participants risks. Prior to initiating telemedicine for study visits the study team will explain to the participant, what a telemedicine visit entails and confirm that the study participant is in agreement and able to proceed with this method. Telemedicine acknowledgement will be obtained in accordance with the Guidance for Use of Telemedicine in Research. In the event telemedicine is not deemed feasible, the study visit will proceed as an in-person visit. Telemedicine visits will be conducted using HIPAA compliant method approved by the Health System and within licensing restrictions.

- 1: Administration site (arm or thigh), as assigned.

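### The recurrence Cox model in Section 12.5 uses a post-dose response status without saying when it is fixed or how early recurrences are classed, and some codings left open bias the hazard ratio towards benefit

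*Combined protocol and SAP*

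**What the plan says.** Section 12.5 gives the model two sentences. The first is "Cox regression analysis will be conducted to explore the association between time to disease recurrence and vaccine-induced immune response status". The second is "Patient baseline characteristics including disease stage and history of treatment will be adjusted in the analysis". Neither gives a date for the status, a time origin, or a rule for a patient who recurs before being sampled.

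Other sections do not settle it:

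- **Status.** Section 12.1 offers two candidates and ties neither to the Cox model. One is a time: "The primary endpoint is the immune response rate at the time of the fourth follow-up measurement", which is Month 6 in calendar order. The other is an individual response "defined as the maximum increase in antigen-specific T cell number or proliferation index after administration of TA-CIN", above 1.8 SD and at least 2-fold, with no last sampling time.
- **Number of draws.** Section 12.1 counts 4 post-treatment measurements and 12.5 counts 5. The Section 10 calendar row "Evaluation of HPV16 E6, E7-Specific CD8" T cells shows 6: Weeks 5, 9 and 11-13, and Months 6, 12 and 24.
- **Clock.** Section 6.10 says "Patients will be followed for 24 months after initiation of study treatment or until death, whichever occurs first", and 6.5 counts the late visits from first dose. Time to recurrence itself is not defined.
- **Recurrence and sampling.** In Section 6.9, "treatment may continue for a total of three vaccinations or until one of the following criteria applies", and disease recurrence heads that list. Section 10 adds: "Research samples will be collected at the discretion of the PI based on availability of supplies and safety of patient and staff".

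**The concern.** A status that can only be acquired by staying recurrence-free long enough to be sampled should not be treated as known at first dose. If it is, responders carry recurrence-free time by construction, and patients who recur early collect in the non-responder group. This is immortal-time bias. Adjustment for stage and treatment history does not remove it, because it comes from when patients are classified and not from differences at baseline. Taking status at the fourth measurement does not cure it either, unless earlier recurrences are excluded.

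This is the only planned analysis linking immune response to clinical outcome (objective 2.3.4). As written, the coding could be chosen with the data in hand, and some of the available codings favour the vaccine when there is no true association.

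**Working it through.** The plan states no event count or HR for this model, so there is no figure to reproduce. The check asks what HR each coding gives when recurrence is independent of response (true HR = 1).

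**Inputs.** From the documents: draws at months 1, 2, 2.75, 6, 12 and 24 (calendar); 24 months of follow-up; response 36% (the 9/25 in 12.2) or 55% (midpoint of 45% and 65% in 12.2). Assumed: constant recurrence hazard with 20% or 40% recurring by 24 months; first responses either spread evenly over the draws or 80% by Week 11-13.

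**Hand calculation: Month 6 status, earlier recurrences coded as non-responders, clock from first dose.** Let R be recurrence by 24 months, λ = −ln(1−R)/24, S(t) = exp(−λt) and p the response rate.

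- Responders: events p[S(6)−S(24)]; person-months p{6·S(6) + [S(6)−S(24)]/λ}.
- Everyone: events R; person-months R/λ. Non-responders by subtraction.

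| | R = 20%, p = 36% | R = 40%, p = 55% |
|---|---|---|
| λ per month; S(6) | 0.0093; 0.9457 | 0.0213; 0.8801 |
| Responders: events / months | 0.0525 / 7.686 = 0.00683 | 0.1541 / 10.143 = 0.01519 |
| Non-responders: events / months | 0.1475 / 13.825 = 0.01067 | 0.2459 / 8.651 = 0.02843 |
| Rate ratio | **0.64** | **0.53** |

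The true ratio is 1. The other two combinations of R and p give 0.56 and 0.62.

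**Simulation, same assumptions.** 400,000 patients per scenario (300,000 for the five-draw row), Monte Carlo error about 0.01 on the HR. Recurrence is recorded (1) when it occurs, (2) at the next calendar visit with that visit's draw counted, or (3) only at 6-monthly scans with the draw first. If the draw in (2) is not counted, column (1) applies.

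| Fixed status, unsampled recurrences = non-responders | (1) | (2) | (3) |
|---|---|---|---|
| Maximum to Week 11-13 | 0.81-0.87 | 0.89-0.93 | 0.99-1.01 |
| Maximum to Month 6 | 0.73-0.83 | 0.85-0.92 | 0.99-1.01 |
| Maximum over five draws (to Month 12) | 0.66-0.81 | not run | 0.90-0.97 |
| Maximum over all six draws | 0.49-0.76 | 0.67-0.87 | 0.70-0.92 |
| Month 6 draw alone | 0.54-0.64 | 0.74-0.81 | 0.99-1.01 |

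In column (1), the six-draw range narrows to 0.67-0.76 if responses are mostly early.

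**Baseline adjustment.** Adding two prognostic baseline factors (assumed prevalence 50%, HR 2.5 and 1.5) leaves column (1) almost unchanged: 0.80-0.87 to Week 11-13, 0.72-0.82 to Month 6, 0.48-0.75 for all six draws and 0.53-0.63 for Month 6 alone.

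**Codings without bias.** Draws continued after recurrence 0.99-1.01; landmark 0.98-1.02; time-dependent response 0.99-1.02.

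**Wider assumptions.** With 24-month recurrence of 20%, 35% or 50% and response of 45% or 65%, no later draws and recurrence recorded as it occurs, the HR is 0.43-0.74 for all six draws and 0.50-0.66 for Month 6 status. The direction is the same in all 12 scenarios. A landmark gives 0.97-1.03.

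**Trials of 15 patients under the null, first responses spread evenly.** Share pointing towards protection (trials with no usable comparison, 0-10%, excluded):

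| Coding | (1) | (2) |
|---|---|---|
| To Week 11-13 | 57-61% | 53-56% |
| Fourth measurement | 66-77% | 58-64% |
| All six draws | 68-79% | 62-68% |

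A landmark gives 49-54%.

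**Precision.** Expected events are 15 × 0.20 = 3 to 15 × 0.40 = 6. The 95% CI factor either side is exp(1.96/√(d·p(1−p))): d = 3, p = 0.36 gives 10.6; d = 6, p = 0.55 gives 5.0.

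**The case against.** The strongest reply is that the protocol does not stop sampling at recurrence. Section 6.9 ends vaccination only, 6.10 follows everyone to 24 months or death, and the calendar puts no recurrence-free condition on the Month 6, 12 and 24 draws. If those draws are taken and recurrence does not affect response, the bias is near nil. That is correct, and the fair wording is that comparable sampling after recurrence is not assured. The discretion clause in Section 10 concerns supplies and safety and does not mention recurrence, but it still leaves later draws optional. A patient who recurs before the third dose also receives fewer doses, which may lower her measured response.

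Second, the largest figures assume that recurrence is recorded as it occurs. Section 1 describes scans every 6 to 12 months and when clinically indicated. With scans only every 6 months, windows to Month 6 show no bias and the five-draw window shows 0.90-0.97; with 12-monthly scans the five-draw figure is 0.99-1.01. Symptom-detected recurrences would fall between columns (1) and (3). This limits the size but does not remove the bias.

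Third, the six-draw window matches neither 12.1 nor 12.5, and the 15-patient percentages use only evenly spread first responses, although the last dose is at Week 9. The 68-79% is therefore an upper-end figure.

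Fourth, a first-dose clock is a reasonable reading of 6.5 and 6.10, so the missing time origin matters less than the missing status date and the missing rule for early recurrences.

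Fifth, with early status the problem group is often empty: the chance that none of 15 patients recurs before Week 11-13 is S(2.75)^15, which is 0.943^15 = 42% to 0.975^15 = 68%. With 3-6 events the estimate is very imprecise in any case. That limits the consequence; it does not make an avoidable bias acceptable.

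**Conclusion.** The concern holds. Section 12.5 leaves open when status is fixed, the time origin and the class of patients who recur before sampling, and no other section supplies them. Carrying the open-ended maximum in 12.1 into the model as a fixed covariate, or using Month 6 status with earlier recurrences counted as non-responders, can give an HR below 1 with no true association.

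The size runs from none to substantial. It depends on whether draws continue after recurrence, how recurrence is ascertained and how late the response window runs. The recurrence rate, the constant hazard and the timing of responses are assumptions. The direction is firmer than the size: in every scenario where a bias appears, it is towards benefit.

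The practical impact is modest. The analysis is exploratory and does not affect the choice of injection site, safety or stopping. A lean of this size could not be seen in one trial of 15, so the coding should be set beforehand. This should be corrected, but it does not threaten the trial's main conclusions.

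**What to change.** Add to 12.5 one of the following:

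- **Landmark.** Response status by the 12.1 threshold is fixed at one named early visit, for example Week 11-13. Only patients recurrence-free at that visit enter the model, the clock starts there, and earlier recurrences are listed separately. If the team prefers the fourth measurement, to keep one responder definition with 12.1, the same exclusion and clock rule remove the bias at Month 6.
- **Time-dependent covariate.** Response switches on at the visit where it is first met. This keeps every patient.

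The same edit should state which draws count, since 12.1, 12.5 and the calendar give 4, 5 and 6.

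The cost is wording and minor programming, with no new data. The landmark loses early recurrences. Under the 20-40% assumption, 15 × [1−S(2.75)] is 0.4-0.9 patients (13-14% of recurrences) at Week 11-13, and 15 × [1−S(6)] is 0.8-1.8 patients (27-30%) at Month 6.
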